#### **Data Storage and Confidentiality**

Data recorded from this study will be organized in REDCap. Participant medical information will only be available to the principal investigator and research staff as necessary for data analysis. All patient health information will be de-identified and assigned a code. Information linking participants' names, social security numbers and medical record numbers will be stored in a secure location separate from the medical information. No data will be shared to anyone outside of the study team.

#### Adverse Event Reporting

Information about any breach of confidentiality will be documented in the electronic data collection system and/or on the paper CRFs, as appropriate. It will be the responsibility of the Principal Investigator to report any Serious Adverse Event (SAE) that occurs during the course

Version 2/26/20

of the prospective data collection to the Institutional Review Board (IRB) within the timeframe specified by NYU SoM.

#### IV. RISK/BENEFIT ASSESSMENT Risk

This study involves risk of medication side effects as well as a breech of confidentiality. Intravenous TXA can cause the following side effects:

- Anxiety
- blurred vision
- changes in vision
- chest pain
- confusion
- cough
- dizziness or lightheadedness
- fainting
- fast heartbeat
- greatly increased or decreased frequency of urination or amount of urine
- increased thirst
- loss of appetite
- nausea or vomiting
- numbness of the hands
- pain, redness, or swelling in the arm or leg
- sudden shortness of breath or troubled breathing

Rare side effects include:

- Convulsions or seizures
- Orthostatic hypotension
- sweating
- trouble seeing
- unusual tiredness or weakness.

## Protection against Risks

Patients will be screened for any contraindication to aspirin or Percocet use.

The patients will stay in the recovery unit a minimum of 3 hours after surgery as the mean duration of the effect of TXA is 3 hours and be monitored by the recovery unit nurses[3, 12]. Patients will be instructed to call the principal investigator and visit the emergency department if there is are any symptoms of calf swelling or chest pain within the first seven days following surgery.

Additionally, all patients will be de-identified and given a code. Information linking the patient codes to the participants' names and medical record numbers will be stored in a secure location separate from the medical information. Access to the information linking the linkage codes with participant identifiers shall be restricted.

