Information to be recorded pre-operatively includes age, sex, height, weight, BMI, and American Society of Anesthesiology (ASA) classification. Intra-operative information will also be recorded, including operative time, and estimated blood loss. During the surgery, a suction device is utilized to remove excess blood from the surgical site and sucked into the suction drain and placed into a measuring cup. We will measure the perioperative blood loss by looking at the measuring cup and seeing how much blood is inside. The objective is to have the average blood loss of the cohort receiving TXA less than the cohort not receiving TXA. Knee swelling postoperatively will be measured using the swelling ratio. The swelling ratio is defined as the circumference of the operative limb divided by the circumference of the contralateral limb. Pain severity scores at rest will be assessed by use of a visual analog scale (VAS; 0 = no pain, 10 =worst pain imaginable) at 0.5, 1, 1.5, 2, 4, 6, 24, and 48 hours as well as 7 days after surgery. Percocet consumption will be recorded at 24 hours, 1 day, 2 days and 7 days after surgery. Incidence of TXA-related side effects (nausea/vomiting, itching, anxiety, increased thirst, rapid heartbeat) in the first 24 hours will be noted. Time to discharge from the post-anesthesia care unit (PACU) and time to discharge from the hospital will be recorded. Patients will be in the study a duration of two weeks, until their post-operative follow up visit.

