## **Data and Safety Monitoring Plan**

Data monitoring will be done by [name], the anesthesiologist, and [name], the principal investigator will oversee the conduct of the study. They will review the following accumulated data quarterly.

They will monitor whether or not:

- 1. Collection and storage of patient data was performed in a sensitive and secure manner, as defined in the informed consent form and protocol, ensuring information is stored on REDCap.
- 2. All study activities were conducted with primary emphasis on patient care and wellbeing, ensuring the patients are not in discomfort and have an abnormally high VAS following the surgery.
- 3. If there were any adverse events, and if so were addressed appropriately and per protocol
- 4. The risk/benefit to patients has remained the same throughout the course of the study.

The study will be stopped if there are unexpected severe AE's in more than one patient. Adverse events will be defined as negative reactions to the intravenous TXA during or after surgery, including seizures, vision problems. We will submit summaries of data and safety monitoring annually.

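### The one post-discharge call instruction does not match the protocol's own adverse event definition, risk list or two-week participation, and no other reporting route is specified

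*Combined protocol and SAP*

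**What the plan says.** Protection against Risks: "The patients will stay in the recovery unit a minimum of 3 hours after surgery", because the mean effect of TXA is given as 3 hours. After that, patients are to call the principal investigator and visit the emergency department for "any symptoms of calf swelling or chest pain within the first seven days following surgery".

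Data and Safety Monitoring Plan: "Adverse events will be defined as negative reactions to the intravenous TXA during or after surgery, including seizures, vision problems". No time limit is attached. The same section says: "The study will be stopped if there are unexpected severe AE's in more than one patient". The anesthesiologist and the principal investigator review accumulated data quarterly.

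Risk: the listed side effects include "sudden shortness of breath or troubled breathing", changes in vision, fainting, and pain, redness or swelling in a limb. Convulsions or seizures are listed as rare.

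Methods and Procedures: "Patients will be in the study a duration of two weeks, until their post-operative follow up visit". TXA-related side effects are noted for the first 24 hours, from a list of nausea or vomiting, itching, anxiety, increased thirst and rapid heartbeat.

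Adverse Event Reporting: the principal investigator must "report any Serious Adverse Event (SAE) that occurs during the course" of prospective data collection to the IRB.

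**The concern.** Patients can leave recovery after about 3 hours, so most of the period at risk is spent outside the hospital. What the investigators learn then depends on what patients are asked to report and what staff ask them. The one stated instruction is narrower than the rest of the plan in both symptoms and time.

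Followed as written, the protocol gives no stated means by which the investigator would hear of breathlessness on day 5, or of calf swelling on day 10. The quarterly review, the IRB reporting duty and the stopping rule can act only on events that someone has reported. A rule that needs a second affected patient is sensitive to a single missed report.

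**Working it through.** The plan gives no figure to reproduce on this point. The check is a comparison of sections, followed by a labelled illustration.

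**Step 1: symptoms.**

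| Event | Monitoring plan definition | Risk list | 24-hour list | Call instruction |
|---|---|---|---|---|
| Seizures | named | yes (rare) | no | no |
| Vision problems | named | yes | no | no |
| Sudden breathlessness | not named | yes | no | no |
| Chest pain | not named | yes | no | yes, to day 7 |
| Calf or limb swelling | not named | yes | no | calf only, to day 7 |

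The call instruction covers 0 of the 2 events that the monitoring plan names.

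**Step 2: window.** Participation is two weeks, or 14 days, and the instruction covers 7. Uncovered: 14 − 7 = 7 days, and 7/14 = 50%. This takes the two weeks in Methods and Procedures at face value. Study Design speaks of a one-week follow-up visit. If participation in fact ended there, the time gap would close, but the symptom gap in Step 1 would not.

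**Step 3: other contacts.** The contacts described after the first 24 hours are:
- pain ratings at 24 and 48 hours and on day 7;
- Percocet use on days 1, 2 and 7;
- knee swelling at the one-week visit;
- the follow-up visit that ends participation.

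None is described as an adverse event enquiry or linked to the monitors. Adverse Event Reporting says what the principal investigator does with a serious event, but not how one is first detected.

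**Step 4: delay.** If an event first came to light at a quarterly review, the wait could reach 365.25/4 ≈ 91 days.

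**Step 5: illustration of the stopping rule.** Let p be the true rate of qualifying events in the 55 TXA patients and c the share that reaches the monitors. With q = p × c:

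P(2 or more seen) = 1 − (1 − q)^55 − 55 q (1 − q)^54

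For p = 2% and c = 1: 1 − 0.3292 − 0.3695 = 0.301. For p = 2% and c = 0.5 (q = 0.01): 1 − 0.5754 − 0.3196 = 0.105.

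| True rate p | All reported | Half reported |
|---|---|---|
| 1% | 0.105 | 0.031 |
| 2% | 0.301 | 0.105 |
| 3% | 0.494 | 0.200 |
| 5% | 0.768 | 0.401 |

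The documents give neither p nor c; both are assumptions. The table applies only if the events count as unexpected and severe. It shows the direction of the effect and is not an estimate for this trial.

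**The case against.** **The lists serve different purposes.** The Risk section includes minor effects such as thirst and sweating, and nothing says patients must phone about each one. Nurse monitoring while the drug acts, followed by a targeted warning, is a coherent design. This stands in part: the call list need not equal the risk list, and the stated 3-hour effect makes a late seizure a weaker example than breathlessness or calf swelling. But the seven-day instruction itself shows that later events are in view, and the two events named for monitoring have no stated route after discharge.

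**Patients may be told more elsewhere.** A reader might infer that patients are not told to report these events. The documents do not support that, because the consent pages were removed and wider instructions there cannot be ruled out. What can be said is that the protocol text contains only this one.

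**Routes exist.** A reader might infer that such events cannot reach the monitors promptly. That also goes too far. The day 1, 2 and 7 contacts and the follow-up visit could reveal an event. The investigator's duty to report serious events covers the whole data collection period, and the principal investigator is also a monitor. The gap is that no route to first detection is specified.

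**The stopping rule may not apply.** It concerns unexpected severe events, and seizures, vision changes and breathlessness are all listed risks. A reader might infer that a missed seizure would keep the rule from triggering. The text does not establish that a listed risk can count as unexpected, so this argument is only conditional.

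**Seven days fits the one-week visit.** This is fair. Study Design and Methods and Procedures differ on the timing of the follow-up visit, and that belongs in the reconciliation.

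**Conclusion.** The point holds as an inconsistency between sections with a practical consequence. The protocol's only patient-initiated safety instruction names neither of the two events in its adverse event definition, omits listed risks such as sudden breathlessness, and covers 7 of 14 days if participation lasts two weeks. Systematic side-effect capture ends at 24 hours and does not list these events. No route is therefore specified by which they, or any event after day 7, reach the principal investigator and the monitors after discharge.

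This rests on the protocol text alone, on the two-week participation, and on reading the later contacts as limited to the purposes described for them. How many events would be missed cannot be estimated, since the documents give no event rates, timing or reporting shares. The effect on the stopping rule is unsettled while the meaning of unexpected is unclear. The mismatch should be corrected because it concerns patient safety and costs little to resolve; it does not show that events have been or will be lost.

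**What to change.** Reconcile Study Design, Methods and Procedures, the Data and Safety Monitoring Plan, Adverse Event Reporting, Risk, and Protection against Risks on two matters: which post-discharge events patients are asked to report, and for how long. The symptoms and the window, including any advice on emergency care, are for the clinical investigators to decide. Check the result against whatever the consent form tells patients.

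Add that each reported event is entered in REDCap, which the study already uses, and passed to the two existing monitors when it is received.

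The cost is a minor amendment of about a sentence, with matching patient instructions. It needs no new visit, procedure or staff. The downside is possibly a few more calls about non-specific symptoms.

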## Potential Benefits to the Subjects

#### Version 2/26/20

Patients may experience less pain post-operatively, and may require less narcotics use, which has a steeper side-effect profile. However, these benefits cannot be guaranteed.

Additionally, it is the hope of the research team that results of this study will benefit future patients and their physicians by providing more information regarding the use of acetaminophen after surgery. This will allow for a more open and informed dialogue, and possibly a change standard of care treatment.

## V. INVESTIGATOR'S QUALIFICATIONS AND EXPERIENCE

The CV, medical license, and human subjects' tutorial completion report are attached for all investigators who are participating in this study. All research personnel have medical research experience and are qualified to participate in this quality study. Most importantly, staff have been properly educated and certified with CITI training to conduct research in a matter that will maintain full patient confidentiality. The research coordinator for this study is trained in GCP principles and practices and will be responsible for compliance with GCP guidelines for all study investigators and research assistants.

#### VI. SUBJECT IDENTIFICATION, RECRUITMENT AND CONSENT/ASSENT Method of Subject Identification and Recruitment

Appropriate patients, who meet all of the inclusion criteria and none of the exclusion criteria, who require a BTB ACL reconstruction, will be identified from the clinical offices of the investigator surgeons.

#### **Process of Consent**

Written consent will be obtained from subjects who are eligible candidates for BTB ACL reconstruction based upon their medical condition (as determined by their physician). The consent process will take place during the office visit when it is determined necessary to perform the procedure—at which time the investigator has determined subject's voluntary participation has been upheld. Subjects will be informed about the study and the intended purpose. They will be given the opportunity to ask questions and receive thorough explanations. They will be made aware of the possible risks and anticipated benefits. They will also be informed of alternative procedures. Subjects will then be given another opportunity to ask questions and agree or disagree to consent.

#### Subject Capacity

All subjects enrolled in this study will have capacity to provide informed consent.

#### **Consent Forms**

Written consent will be obtained from the patient.

#### **Documentation of Consent**

Signed consent forms will be kept in a binder and stored in a locked file cabinet.

#### Costs to the Subject

Subjects will not incur any additional financial costs as a participant in this study.

Version 2/26/20

### **Payment for Participation**

No payments/reimbursements will be provided to subjects for their participation in this study.

